Telehealth has immense potential to improve healthcare quality by improving patient satisfaction and clinical outcomes while minimizing adverse events. Postoperative patient satisfaction is an indicator of overall surgical quality of care.^{4,6} Studies focusing on patient-centered outcomes associated with videoconference technology for delivery of postoperative care following pelvic reconstructive surgery are limited. To date, only two randomized controlled trials have been published evaluating patient satisfaction with telehealth visits in the urogynecologic population.^{4,6} The intervention evaluated by Thompson et al. was limited to telephone visits only for postoperative follow-up.⁴ The study by Lee et al. included only patients undergoing pelvic organ prolapse surgery with a follow-up call placed 48 to 72 hours after discharge and both video and in-person groups returning to the office at 90 days after surgery; patient satisfaction was evaluated at the 30-day in-person versus virtual visit.⁶ Both trials demonstrated that postoperative telehealth visits were non-inferior to traditional in-office visits based on patient satisfaction; with no difference in healthcare utilization, complication rates, or clinical outcomes based on validated questionnaires. Additionally, several studies have demonstrated a positive correlation between patient preparedness for pelvic organ prolapse and/or anti-incontinence surgery and postoperative satisfaction, perioperative outcomes, postoperative symptom and quality of life improvement, and perceived complications.⁸⁻¹⁰

The proposed VIDEO randomized trial will help inform clinical practice regarding the utility and perceived value of videoconferencing for postoperative care of urogynecologic patients by comparing patient satisfaction with virtual video visits and traditional in-office visits after pelvic organ prolapse and/or anti-incontinence surgery. The study will secondarily investigate other important components of healthcare quality, including safety and clinical outcomes, by comparing postoperative healthcare resource utilization and adverse events within 12 weeks after urogynecologic surgery.

B. SPECIFIC AIMS

Primary aim:

- To compare patient satisfaction with their postoperative visit between patients receiving in-office versus virtual-video postoperative visits at 6 weeks after surgery.

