We hypothesize that patient satisfaction with a virtual postoperative visit will be noninferior to patient satisfaction with an in-office postoperative visit

Secondary aims:

- To compare healthcare resource utilization after the postoperative visit up to 12 weeks following urogynecologic surgery between patients receiving in-office versus virtual-video postoperative visits.

We hypothesize that the virtual group will be noninferior to the in-office group based on healthcare resource utilization after the postoperative visit up to 12 weeks following surgery.

- To compare adverse events after the postoperative visit up to 12 weeks following urogynecologic surgery between patients receiving in-office versus virtual-video six-week postoperative visits.

We hypothesize that the virtual group will be noninferior to the in-office group based on adverse events after the postoperative visit up to 12 weeks following surgery.

- To evaluate patient and provider preferences/attitudes toward in-office versus virtual-video postoperative visits

C. RESEARCH PLAN

Overall Study Design

- The study is a randomized controlled noninferiority trial evaluating patient satisfaction with in-office versus virtual-video postoperative visits at six weeks following urogynecologic surgery. We aim to assess whether the intervention of virtual postoperative visit via videoconference technology is noninferior to the standard/traditional in-office postoperative visit for our primary outcome of patient satisfaction. The recruitment period will be 15 months (January 1, 2023 to March 31, 2024). The follow-up period for each participant will be 12 weeks after surgery.

Outcome Measures

- Primary Outcome:
 - Patient satisfaction as measured by the Patient Satisfaction Questionnaire-18 at the 6-week postoperative visit
- Secondary Outcomes:
 - Healthcare resource utilization as measured by patient-initiated phone calls, unscheduled in-person/virtual office visits, emergency room or urgent care visits, and inpatient readmissions after the scheduled postoperative visit up to 12 weeks following surgery
 - Adverse events after the scheduled postoperative visit up to 12 weeks following surgery
 - Patient and provider preferences/attitudes toward virtual or office visits

Eligibility Criteria

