- Emergency department or urgent care visits during the next six weeks following the scheduled 6-week postoperative visit (Y/N); if Y,
 - Total number of ED/urgent care visits (No. of occurrences)
 - Date of ED visit #1 (MM/DD/YYYY)
 - Reason/s for ED visit
 - Outcome of ED visit (discharge, readmission, reoperation, other-specify)
 - Date of ED visit #2 (MM/DD/YYYY)
 - Reason/s for ED visit
 - Outcome of ED visit (discharge, readmission, reoperation, other-specify)
- Hospital readmissions during the next six weeks following the scheduled 6-week postoperative visit (Y/N); if Y,
 - Total number of hospital readmissions
 - Date of readmission #1
 - Reason/s for readmission
 - Outcome of readmission (discharge, reoperation, other-specify)
 - Hospital length of stay (no. of days)
- Adverse events during the next six weeks following the scheduled 6-week postoperative visit (Y/N); if Y, specify (urinary tract infection, neurologic injury, hemorrhage/hematoma, blood transfusion, wound infection and cellulitis, seroma, abscess, pyelonephritis, sepsis, vaginal fistula, vaginal dehiscence, deep venous thrombosis, pneumonia, drainage of abscess, delayed gastrointestinal injury, delayed genitourinary injury, ileus, small bowel obstruction, pulmonary embolism, myocardial infarction, cerebrovascular accident and stroke, death, mesh complication, readmission, reoperation)
- Power Analysis and Sample Size Calculation
 - The primary outcome of this study is to compare patient satisfaction between patients scheduled for office versus virtual six-week postoperative visits.
 - A priori sample size calculation determined that 100 participants (50 per group) would allow for 80% power to assess a noninferiority margin of 5 points on the

total PSQ-18, with a SD of 10 and significance level of 0.05. A minimum important difference has not been reported for the PSQ-18; however, previous studies using this tool demonstrated SD for total PSQ-18 score ranging between 2.6 and 11.8 and used a 5-point interval for the noninferiority margin.^{6,13} To account for an anticipated attrition rate of approximately 5%, we aimed to enroll a total of 106 participants (53 per group).

- **Statistical Analysis**

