- Patient satisfaction (PSQ-18) total scores, as well scores in each of the 7 PSQ-18 domains, will be treated as continuous data and checked for normality. Healthcare utilization will be analyzed individually (number of phone calls, number of outpatient visits, number of emergency department or urgent care visits, number of hospital readmissions), as well as a composite of all encounter types. Adverse events will be analyzed independently but also as a composite utilizing the Clavien-Dindo Grading System for surgical complications. Attitudes toward office/virtual visits will be analyzed by comparing proportions of patients and providers who prefer a virtual visit, prefer an office visit, or have no preference.
- All analyses will be conducted using an intention-to-treat principle. Baseline demographic and clinical characteristics will be summarized using descriptive statistics. Normally-distributed continuous measures will be summarized using mean and standard deviation (SD), whereas those showing departure from normality will be summarized using median and interquartile range (IQR). Categorical measures will be summarized using number of participants and percentage. The primary end-point analysis will be designed to test whether patient satisfaction with a virtual postoperative visit is noninferior to an in-person postoperative visit, as determined by the total PSQ-18 at the scheduled postoperative visit. Noninferiority would be shown if the lower limit of the two-sided 95% confidence interval for the between-group mean difference in the primary endpoint (i.e., the difference between the mean PSQ-18 total score in the virtual group minus the mean PSQ-18 total score in the in-office group) is more than -5 points. Similar analyses will be performed for each secondary outcome. The noninferiority margin is defined as 5 points for the PSQ-18 total score and 0.5 points for the PSQ-18 domain scores, 10% absolute for composite healthcare resource utilization, and 25% absolute for composite adverse events. Planned exploratory subgroup analyses of patient satisfaction, healthcare resource utilization and adverse events based on surgery level will be additionally performed.
- All statistical analyses will be performed using JMP Pro version 17.0 software (SAS Institute, Cary, NC).
- Data will be managed in REDCap. Statistical support will be provided by the Cleveland Clinic Quantitative Health Sciences.

E. PRIVACY AND CONFIDENTIALITY

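### The 25-point noninferiority margin for composite adverse events has no stated rationale, expected rate or power, and would often accept a doubling of events if the office rate is about 10% or lower

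*Combined protocol and SAP*

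**What the plan says.** The background text before Section B says that the trial will secondarily examine "other important components of healthcare quality, including safety and clinical outcomes". Section B (Specific Aims, secondary aims) turns this into a formal hypothesis, that "the virtual group will be noninferior to the in-office group based on adverse events after the postoperative visit", with follow-up to 12 weeks after surgery.

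Section D (Statistical Analysis) defines the decision rule for the primary outcome by a two-sided 95% confidence limit. It then adds "Similar analyses will be performed for each secondary outcome" and sets the composite margins at "10% absolute for composite healthcare resource utilization, and 25% absolute for composite adverse events". On the composite itself it says "Adverse events will be analyzed independently but also as a composite utilizing the Clavien-Dindo Grading System". It does not say whether any event counts or only events above some grade.

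Section D (Power Analysis and Sample Size Calculation) concerns the PSQ-18 only: "100 participants (50 per group) would allow for 80% power to assess a noninferiority margin of 5 points". The 5-point margin is supported there by earlier studies. No section gives a reason, an expected event rate or a power for the adverse-event margin. The background reports that two earlier trials found no difference in complication rates, but gives no rates.

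**The concern.** An absolute noninferiority margin can be judged only against the event rate expected in the control arm. A 25-point margin accepts, at the limit, a true virtual rate just under 35% against 10% in the office arm, or just under 30% against 5%. The events recorded for the twelve-week period range from urinary tract infection to sepsis and pulmonary embolism, and the list ends with "cerebrovascular accident and stroke, death, mesh complication, readmission, reoperation".

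If few patients have an event after the six-week visit, the trial could report that virtual visits are noninferior for adverse events when events had in fact doubled. Readers would take that as reassurance about safety. Because no rate is stated, they could not tell from the plan whether passing the test means much.

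**Working it through.** **1. The plan's own sample size.** Inputs from Section D: margin 5, SD 10, 80% power, significance level 0.05. Taking 0.05 as one-sided:

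n per arm = 2 × (1.645 + 0.842)² × 10² / 5² = 49.5, rounded up to 50. Allowing for 5% attrition, 100 / 0.95 = 105.3, rounded up to 106.

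Both stated figures reproduce. Neither uses an adverse-event rate.

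**2. Assumptions for the adverse-event test.** The plan does not state these in full:
- 25% absolute means 25 percentage points.
- The composite is the proportion of patients with at least one event.
- There are 50 patients per arm.
- The difference is virtual minus office. Because more events are worse, noninferiority requires the upper two-sided 95% limit to be below 25 points.
- No interval method is named, so both Wald and Newcombe limits are shown.

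**3. Observed results that pass.** The Wald upper limit is d + 1.96 × √[p_v(1−p_v)/50 + p_o(1−p_o)/50]. The Newcombe upper limit is d + √[(u_v − p_v)² + (p_o − l_o)²], where u_v is the upper Wilson limit for virtual and l_o the lower Wilson limit for office.

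- 5/50 versus 10/50, Wald: 0.10 + 1.96 × √(0.0032 + 0.0018) = 0.239. Newcombe: 0.10 + √(0.1304² + 0.0565²) = 0.242. **Passes.**
- 5/50 versus 11/50: 0.262 Wald, 0.264 Newcombe. **Fails.**
- 2/50 versus 8/50, Wald: 0.12 + 1.96 × √(0.002688 + 0.000768) = 0.235. Newcombe: 0.12 + √(0.1251² + 0.0290²) = 0.248. **Passes**, with a fourfold observed excess.

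**4. Chance of declaring noninferiority.** For each pair of true rates, the binomial probabilities of all pairs of counts whose upper limit is below 0.25 were summed. The office rates are assumed.

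| Office rate | True doubling: Wald / Newcombe | No true excess: Wald / Newcombe |
|---|---|---|
| 5% | 95.4% / 92.6% | 99.9% / 99.8% |
| 10% | 57.5% / 55.2% | 98.3% / 97.6% |
| 15% | 23.4% / 24.4% | 93.6% / 93.2% |
| 20% | 8.0% / 9.2% | 87.8% / 88.3% |
| 30% | not computed | 78.3% / 80.3% |

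With 53 per arm, the doubling results are 96.1% / 93.0%, 60.1% / 56.9%, 24.3% / 25.3% and 8.5% / 9.5% for office rates of 5%, 10%, 15% and 20%.

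**5. Margin or sample size?** A true 10% versus 20% passes 55-58% of the time at 50 per arm, 84-85% at 100 and 99% at 200. A difference inside the margin passes more often as the arms grow, so the leniency comes from the margin.

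**The case against.** The strongest reply is that the documents show a missing justification, not a margin proved too lenient. That stands. The event list is broad, no section shows a rate of 10% or lower, and at 15-20% a doubling usually fails. At 30% in both arms the power of 78-80% is an ordinary design value. Doubling is also a yardstick chosen here, not in the plan. Any absolute margin admits large relative increases at low rates, and the error rate at the 25-point boundary stays close to nominal (2.6% to 4.4% at office rates of 10% or lower). The test does what was specified.

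A reader might go further in two ways that the documents do not support. The first is that a noninferior finding is nearly assured at any low rate. That fits only about 5% or lower; at 10%, a doubling would fail more than 40% of the time. The second is that the 10-point utilization margin proves 25 wrong. Utilization is defined "as measured by patient-initiated phone calls, unscheduled in-person/virtual office visits, emergency room or urgent care visits, and inpatient readmissions", so it counts even phone calls and shares readmission with the adverse-event list, and the difference in margins is unexplained. But the plan does not define membership of the adverse-event composite or say what the 10% is a proportion of, and the 10-point figure may itself be unrealistic at this size. The contrast is context only.

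It can also be said that this is a secondary outcome and that events are analysed individually as well. Both are true and limit the weight of the point. Neither repairs a composite statement of noninferiority on safety that rests on an unexplained margin.

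**Conclusion.** The point holds in conditional form. The plan prespecifies a formal safety claim against a 25-point margin with no rationale, expected rate or power. Under the assumptions above, the rule would label observed results of 5/50 versus 10/50, or 2/50 versus 8/50, noninferior. If the true office rate is about 10% or lower, a true doubling would be declared noninferior more often than not. At 15-20% it would usually be caught.

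Confidence is medium, because the size depends on the unstated rate and on how the composite is defined. The point merits correction but does not touch the primary PSQ-18 conclusion.

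**What to change.** By a dated, disclosed amendment before comparative data are analysed:

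1. In Section B, replace the adverse-event noninferiority hypothesis with a descriptive comparison of the arms.
2. In Section D (Statistical Analysis), delete the 25-point margin.
3. In the same section, add the words *except adverse events* to the sentence "Similar analyses will be performed for each secondary outcome". Without this, the plan would still call for the deleted test.
4. Add: *Composite adverse events after the postoperative visit will be reported by arm with the risk difference (virtual minus office) and its 95% CI as a descriptive safety result; no noninferiority statement will be made.*

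The planned recruitment end (March 2024) and completion goal (June 2024) mean that this route may already be closed. If comparative data have been analysed, keep the prespecified test and report the risk difference and its interval beside it. State that the margin had no prespecified rationale or expected rate, and that passing it does not by itself exclude a doubling of events.

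The cost is a few wording changes, with no new patients or data. The downside is that one formal secondary noninferiority claim is given up; the estimate and its interval remain.

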 - Stratified block randomization will be used to ensure that the number of participants is equally distributed among the study groups and stratified by surgery level (major, minor). The allocation sequence will be generated with block size of 4 using computer software. Randomization will be implemented with the REDCap Randomization module. Randomization schedule can only be accessed by a research personnel not directly involved in patient care. The patient's 6-week postoperative visit will be scheduled according to her assigned group.
- Study instruments:
 - Study instruments will be administered at the preoperative visit and the 6-week postoperative visit. The questionnaires for this study include the Patient Preparedness Questionnaire (PPQ), the Patient Satisfaction Questionnaire-18 (PSQ-18), and modified patient and provider preference questionnaires entitled, Patient Postoperative Visit Questionnaire and Provider Postoperative Visit Preference Questionnaire.
 - The PPQ will be administered during the preoperative visit to assess patient knowledge and preparedness for surgery, which has been demonstrated in other studies to impact postoperative satisfaction, perceived complications, and drug utilization.¹⁰⁻¹¹ The PPQ is a 11-item questionnaire scored on a six-point Likert scale and has responses ranging from 1 (strongly agree) to 6 (strongly disagree).⁹ The questionnaire for this study will utilize the same six-point scale with a reversed scoring system, ranging from 1 (strongly disagree) to 6 (strongly agree). Although there are currently no validated measures to assess surgical preparedness in urogynecology, the PPQ has been used in several studies assessing surgical preparedness in women undergoing pelvic organ prolapse and/or stress urinary incontinence.^{8,12} These studies utilized the same cutoff score for question 11 (i.e., an answer of "strongly agree" to the question "overall, I feel prepared for my upcoming surgery") to define meeting criteria for preoperative preparedness.
 - The PSQ-18 will be administered after the 6-week postoperative virtual or in-office visit to assess patient satisfaction with their postoperative visit. The PSQ-18 is a

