validated 18-item questionnaire developed to evaluate satisfaction with medical care in seven domains, namely general satisfaction, technical quality, interpersonal manner, communication, financial aspects, time spent with doctor, and accessibility and convenience. Responses are scored on a five-point Likert scale, ranging from 1 (strongly disagree) to 5 (strongly agree). The total score for the questionnaire ranges from 18 (dissatisfaction with medical care) to 90 (highest satisfaction with medical care). The questionnaire has been studied extensively and used as a valid and reliable measure of satisfaction in a variety of settings, including postoperative care after pelvic organ prolapse surgery and minimally invasive gynecologic surgery.⁵⁻⁶

- Currently, there are no validated tools to assess patient or provider attitudes towards telemedicine in urogynecology. A customized patient questionnaire "Patient Postoperative Visit Questionnaire" will be administered after the six-week postoperative visit to assess patient's preference/attitude towards virtual and office visits. The items in this questionnaire were adapted from a survey used in a cross-sectional study of patients and clinicians (psychiatry, neurology, cardiology, oncology, and primary care) participating in telehealth virtual video visits in an academic health system.³ The questionnaire was originally developed by the MGH Center for TeleHealth leadership and Mongan Institute Health Policy Center research team and consists of 7 comparative questions about office visits and virtual video visits. The customized survey includes an open-ended question, allowing the patient to select their preference for in-person or virtual visits for future postoperative visits and to specify their reason/s.
- A provider preference questionnaire "Provider Postoperative Visit Preference Questionnaire" will be administered to the surgeon or advanced practice provider after completion of the six-week postoperative visit to assess provider preference/attitudes. The questionnaire was adapted from the provider survey utilized by Donelan et al. and consists of 10 comparative questions about office visits and virtual video visits.³

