- All questionnaires can be completed either with paper forms or electronically through Research Electronic Data Capture (REDCap), depending on patient/provider preference. Study participants will be reminded within 48 to 72 hours after their visit regarding completion of their questionnaires by telephone call using a standardized phone script or by text or email message after their preoperative visit and their 6-week postoperative visit. Reminders for survey completion will be sent up to two times.

- Preoperative Visit
 - The preoperative visit will take place per our standard protocol, which includes a thorough discussion of the surgical purpose, alternatives, benefits, risks/complications, and postoperative expectations. Following informed consent, study-related procedures during the preoperative visit include study randomization, and scheduling of postoperative visits per study protocol. The PPQ will also be administered during this visit.
- Postoperative Visit (6 weeks)
 - Prior to the 6-week postoperative visit, a study investigator will initiate a reminder to the participant by phone, email or text to remind her of her upcoming appointment using a standard script. A checklist of discussion points will be used to standardize counseling and evaluation during the 6-week postoperative visit. Both office and virtual visits will be conducted in the same manner: The provider

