will inquire about any concerns the patient has regarding recovery, followed by any unanticipated healthcare encounters at outside facilities. These outside healthcare encounters will be documented by the provider in their Epic note to facilitate data collection by the study investigators. The provider will review key aspects of postoperative care (bowel function, urinary function, presence of vaginal bleeding, dietary status, and ambulatory status), postoperative instructions and precautions, findings and procedures done during surgery, and pathology results (if applicable). The provider will then visually examine surgical sites and document their findings in their Epic note. The provider will inquire about any additional questions from the patient and perform additional evaluation/treatments per standard of care. The PSQ-18 and the Patient Postoperative Visit questionnaire will be administered after this visit. The patient may be contacted for up to two times by a study investigator via phone, text or email within 48 to 72 hours after the visit regarding completion of study questionnaires using a script.

- **Provider Recruitment and Study Procedures**
 - Surgeons and advanced practice providers will be educated about the study during the Urogynecology Section Research Meeting as part of the provider recruitment process.
 - After the six-week virtual or in-office visit, the provider will fill out the Provider Information Sheet and the Provider Postoperative Visit Preference Questionnaire. The provider will complete the questionnaire at the end of the visit. If this is not feasible, the provider will be sent a text reminder for up to two times to their Cleveland Clinic issued phone number within 48 to 72 hours after the visit.

	Preoperative Visit	Day of Surgery	Postoperative Visit (6 weeks)	End of study follow-up (12 weeks after surgery)
Questionnaire: PPQ	X			
Questionnaire: PSQ-18			X	
Questionnaire: Patient Postoperative Visit			X	
Questionnaire: Provider Postoperative Visit Preference			X	
Data collection: Demographic and baseline clinical characteristics	X			
Data collection: Perioperative characteristics		X		
Data collection: Postoperative healthcare resource utilization, adverse events			X	X

D. DATA ANALYSIS PLAN

- Data Collection

- A) Demographic data will include the following:
 - Date of preoperative visit (MM/DD/YYYY)
 - Route of preoperative visit with surgeon (in-office/virtual)
 - MRN
 - Age (years)
 - Race
 - Ethnicity

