Protection of each subject's personal health information will be a priority in this study. One master Excel file containing subject personal information including name and medical record number will be kept in a password-protected file, on a designated protected research drive on a password-protected computer in a locked office at the Cleveland Clinic. In that file, each subject will be assigned a subject identification number that will be used for the purposes of data collection in order to de-identify subjects. All paper forms used for data collection will be kept in a research cabinet dedicated to this project which will be locked at all times, in a

locked office at the Cleveland Clinic. All forms will contain de-identified information; identification numbers will correspond to the subjects listed in the master Excel file. All study data will be transferred and managed electronically using REDCap. Each subject will be entered into REDCap using the assigned identification number from the master Excel file.

F. DATA/SAMPLE SHARING

Not applicable

G. ADVERSE EVENTS AND DATA MONITORING

Any adverse event or unanticipated events will be reported as soon as feasible to the IRB using IRB WebKit. Examples of adverse events include inability to attend the postoperative visit due to technological issues (If the visit cannot be completed due to technological issues, the provider will ensure that the appointment is rescheduled to another time that is convenient and acceptable to the patient). All events will be recorded and kept in a research binder assigned to this study in a locked office. Monthly reviews during the study period will be done by all involved study staff members to ensure that events are not occurring, and if they are, that they are being handled and reported properly. The study will be terminated if patients in the intervention arm have decreased satisfaction of 20% compared to the control arm. This will be assessed monthly at the reviews mentioned above.

H. STUDY TIMELINE

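### The mandatory monthly termination rule has no minimum number of scored questionnaires, so it can end a sound trial on a handful of early scores

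*Combined protocol and SAP*

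**What the plan says.** The rule is in section G (Adverse Events and Data Monitoring): "The study will be terminated if patients in the intervention arm have decreased satisfaction of 20% compared to the control arm". On timing, "This will be assessed monthly at the reviews mentioned above". On who takes part, "Monthly reviews during the study period will be done by all involved study staff members".

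Section G does not name the satisfaction measure, the base of the percentage, or the number of patients needed before the rule applies. Section D does not fill the gap: neither the sample size text nor the Statistical Analysis text mentions this rule or any interim look.

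Two of the missing items can be inferred. The primary outcome is the PSQ-18 total, scored 18 to 90 and analysed as continuous, so it is the obvious measure. Statistical Analysis labels two of its margins as absolute percentages and section G does not, so 20% most naturally means relative to the office-arm mean. The minimum number cannot be inferred from anything.

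On access, section C (Randomization) says: "Randomization schedule can only be accessed by a research personnel not directly involved in patient care". Section G has no statement on who may see outcome results by arm.

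**The concern.** The wording is mandatory and the check starts as soon as both arms have a score. In the first month or two of six-week visits, each arm mean rests on a few women. With an SD of 10, a gap of about 15 points between two such means can arise by chance. Followed literally, the rule would then end a trial in which the two visit types are equally satisfactory, and that loss cannot be undone.

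There is a second, smaller issue. The monthly check puts accumulating results on a subjective primary outcome, by arm, before all involved study staff. Some of them have participant contact: "The patient may be contacted for up to two times by a study investigator via phone, text or email" about questionnaire completion. The provider preference questionnaire, itself a secondary outcome, "will be administered to the surgeon or advanced practice provider after completion of the six-week postoperative visit to assess provider preference/attitudes". The visit format cannot be blinded, but accumulating results can be withheld.

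**Working it through.** **Inputs from the documents.** SD 10 for planning, and 2.6 to 11.8 in earlier studies (section D). Margin 5 points. 106 women, 53 per arm, recruited over 15 months (sections D and C). Blocks of 4, stratified by surgery level (section C).

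**Inputs assumed.** Normal scores; office-arm mean 70, 75 or 80 (not in the documents); stop if the virtual mean is at or below 0.8 times the office mean.

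**Plan's own figure.** The rule has no stated operating figure. The sample size reproduces at one-sided 0.05: 2 × 10² × (1.645 + 0.842)² / 5² = 49.5, so 50 per group, and 50 / 0.95 = 52.6, so 53.

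**Pace of the looks.** 106 / 15 = 7.07 women per month, about 3.5 per arm.

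**One look, no true difference.** With common mean μ and n per arm, (virtual mean − 0.8 × office mean) has mean 0.2μ and standard error SD × √((1 + 0.64)/n). The chance of stopping is Φ(−0.2μ / SE). For n = 4, SD 10 and μ = 75: SE = 10 × √(1.64/4) = 6.40, 15 / 6.40 = 2.34, probability 0.96%.

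| Scores per arm at the look (SD 10) | SE | Chance of stopping, μ = 70 / 75 / 80 |
|---|---|---|
| 1 | 12.81 | 13.7 / 12.1 / 10.6% |
| 2 | 9.06 | 6.1 / 4.9 / 3.9% |
| 4 | 6.40 | 1.4 / 1.0 / 0.6% |
| 8 | 4.53 | 0.10 / 0.05 / 0.02% |
| 10 | 4.05 | 0.03 / 0.01 / 0.004% |

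**All monthly looks together (simulation, no true difference).** Starting at 4 per arm, then 8, 11, 15 and so on to 53:
- SD 10: about 0.6 to 1.5% with a first look of 4 per arm, 4 to 6% with 2, and 11 to 14% with 1.
- SD 11.8: about 1.7 to 3.4%, 7 to 10%, and 15 to 19%.
- SD 7, first look 4: about 0.1% or less. SD 2.6, first look 4: about zero.

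These totals barely exceed the single-look figures, so the first look carries almost all the risk.

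**Random arrivals.** With chance arrivals at the planned average rate, blocks of 4 in two strata (70% major surgery, assumed) and 95% of questionnaires scored, the smaller arm has 2 or fewer scores at the first usable look in 40% of trials. False stops are about 2 to 4% at SD 10, 4 to 6% at SD 11.8 and under 1% at SD 7.

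**True deficits, SD 10, first look 4 per arm.** Ranges run over office means 80 to 70.

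| True difference | No minimum | Minimum 8 per arm | Minimum 10 per arm |
|---|---|---|---|
| 0 | 0.6–1.5% | at most about 0.1% | at most about 0.02% |
| −5 | 5–9% | 0.8–2.9% | 0.2–1.2% |
| −10 | 23–39% | 12–28% | 8–22% |
| −15 | 74–93% | 68–91% | 64–90% |
| −20 | above 99% | above 99% | above 99% |

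At SD 11.8 with no true difference, a minimum of 8 leaves at most about 0.5%, and a minimum of 10 about 0.1%.

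**Base of the 20%.** At an office mean of 75, the relative reading is 15 points. A share of the 72-point range is 0.2 × 72 = 14.4, and a share of the 90 maximum is 0.2 × 90 = 18. At a true −15 (SD 10, first look 4) these stop 85%, 90% and 53% of trials.

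**The case against.** The strongest reply is about weight. At the planning SD and planned accrual the false-stop risk is about 1 to 4%, and at the lower SDs in the plan's own range it is negligible. That stands, and it keeps this a modest point. Higher figures need assumptions stacked on one another. For example, adding an assumed wait to surgery of 0 to 3 months gives 5.5 to 8.1% at SD 10. The documents give no such wait, so I do not rest the point on it.

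Several stronger readings are tempting but not supported:
- **That the unstated base makes the rule unworkable.** The two natural readings differ little (85% against 90% at a true −15). The large contrast needs 18 points, a share of the 90 maximum on a scale that starts at 18, which is the least natural reading.
- **That 20% means a drop in the proportion satisfied.** False stops would then be far more frequent, but the plan defines no satisfied/dissatisfied cutoff and treats the PSQ-18 as continuous.
- **That monthly looks inflate the error rate of the noninferiority claim.** They do not. The rule stops only when the virtual arm looks worse, so it can only remove chances to claim noninferiority.
- **That section G breaches the restriction in Randomization.** That restriction controls the allocation schedule. Access to accumulating results is a different matter, so the two texts do not contradict each other.
- **That treating providers will see results by arm.** Their attendance at the reviews is not stated, and section C describes provider recruitment separately from the study investigators' tasks.

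On bias more generally, patients complete the PSQ-18 themselves, reminders follow a script, and "A checklist of discussion points will be used to standardize counseling and evaluation during the 6-week postoperative visit". These safeguards reduce the risk, and no direction or size of bias has been shown.

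**Conclusion.** The point holds in a limited form. A mandatory stopping rule without a minimum number of scores can end a sound trial on very few questionnaires. At SD 10 and planned accrual the chance is about 2 to 4% with random arrivals. With regular looks it runs from about 1% to 14%, depending on whether the first look has 4 women per arm or only 1. At a true deficit equal to the 5-point margin, about a third of the roughly 15 points the rule targets, it stops 5 to 9% of trials.

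These figures rest on an office mean of 70 to 80, normal scores, the relative reading, and the rule being applied literally. The missing measure and base need only a clarification. The question of who sees results by arm is secondary and unquantified. The change is worth making because the loss would be irreversible and the remedy is short.

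**What to change.** In section G, state in one sentence that the rule uses the PSQ-18 total, that the 20% is relative to the office-arm mean, and that it applies only once a stated minimum in each arm, for example 8 to 10, have a scored PSQ-18. Leave the 20% threshold as it is.

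The cost is a few words and slower action on a real early deficit. At planned accrual, 10 per arm is reached about 10 / 3.53 = 2.8 months into the visits. As tabulated above, a minimum of 10 lowers stopping at true deficits of 10 and 15 points but hardly changes it at 20. A minimum of 8 loses less, with slightly more false stops.

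As a secondary step, have the arm comparison made by the statistical group named in Statistical Analysis, or by the research person who holds the randomization schedule. Return only continue or stop to staff who conduct visits, contact participants about questionnaires or complete the provider questionnaire. This adds a small monthly task that the plan's general offer of statistical support does not now specify. Sample size and final analysis are unaffected.
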